- Length of hospital stay defined in days from POD 1 to until hospital discharge excluding death

Safety Measures

The following description were based on the original protocol.

Adverse Events (AE)

An AE is any untoward medical occurrence in a subject to whom an intervention has been administered, including occurrences which are not necessarily caused by or related to that intervention. An AE can therefore be any unfavorable and unintended sign, symptom or disease temporarily associated with study activities. However, this study does not involve an investigational medical device, and all trial interventions are already in routine clinical use for patients undergoing a surgical procedure. The safety of the intervention will be monitored by recording acute adverse events at 24 hours and 30 days after randomization as a trial outcome. These events will be monitored at intervals by the DMEC and will be recorded separately as an AE on the CRF.

Serious Adverse Event (SAE)

A serious adverse event (SAE) is defined as an untoward occurrence that:

- results in death
- is life-threatening
- requires hospitalization or prolongation of existing hospitalization significantly beyond normal inpatient stay for the surgery concerned
- results in persistent or significant disability or incapacity

An SAE occurring to a research participant should be reported to the sponsor where in the opinion of the Chief Investigator the event was:

- Related – that is, it resulted from administration of any of the research procedures, and
- Unexpected – that is, the type of event is not listed in the protocol as an expected occurrence.

This study is an investigation of a perioperative intervention. It is expected that patients undergoing major surgery will suffer complications, with consequences up to and including death. Only complications considered by the Chief Investigator to be *related to the use of study procedures* and not a typical surgical complication should be reported as SAEs.

Study Design

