- All protocol deviations will be documented in a protocol deviation log, which will be reviewed regularly by the trial steering committee to ensure consistency in applying the exclusion criteria.
- The rationale for excluding each participant will be documented in detail.

The primary analyses of the primary and secondary outcomes will be based on the ITT population. The per-protocol population will be used in the safety and sensitivity analysis.

Note: Patients who were randomized and treated, but lost to follow up, will be included to the time of dropout. Patients who withdrew their consent to participate the study will not be included in analysis.

The CONSORT diagram as of January 26, 2024 is presented as follows. The last patient was recruited on December 27, 2023. At the time of formulating this statistical analysis plan, the follow-up per research protocol is ongoing. We anticipated to finish patient follow-up in early February 2024.

We will evaluate the baseline homogeneity using absolute standardized differences. For both primary and secondary analyses, we will correct for baseline factors with ASDs above the threshold determined by the following equation: $1.96 \times \sqrt{(\text{nt} + \text{nc})/(\text{nt} * \text{nc})}$.1 where t is treatment and c is control.

Analysis of the primary outcome

The primary outcome will be evaluated using logistic regression to estimate the odds of postoperative composite complications. A one-sided Z-value < -1.932 will be considered statistically significant.

A sensitivity analysis evaluating an average relative effects model. (Edward J Mascha, Daniel I Sessler. Statistical grand rounds: design and analysis of studies with binary- event composite endpoints: guidelines for anesthesia research. *Anesth Analg*. 2011 Jun;112(6):1461-71. doi: 10.1213/ANE.0b013e31821796d3.)

Analysis of the secondary outcomes

For the secondary analysis of continuous and categorical outcomes in the BOTTOMLINE-CS trial, the following details will outline the statistical methods that will be used. All analyses will be adjusted for unbalanced baseline characteristics and reported with 95% confidence intervals.

- Continuous outcomes will be analyzed using linear regression or generalized linear models as appropriate, depending on the distribution of the data and the study design.
- Composite secondary outcomes will be analyzed using the same approach as the primary outcome.

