- Categorical outcomes will be analyzed using logistic regression for binary outcomes or chi-squared tests for categorical variables with more than two categories.
- Bonferroni-Holm's method will be used for multiplicity adjustment for the p values of those secondary outcomes.

Safety analysis

- This analysis will list all adverse events and serious adverse events that were related to the research procedures.
- The analysis will include rows for each type of adverse event and columns for the intervention group, control group, number of events, percentages, and a comparison column if appropriate.

Sensitivity Analysis

Patients who withdrew from the trial voluntarily will not be included in analysis.

In the sensitivity analyses, we will assess the robustness of the trial findings. These analyses deal with the patients who did not have outcome data and the per-protocol population instead of ITT population. The plan for conducting sensitivity analyses in the BOTTOMLINE-CS trial are outlined as follows:

Missing Data:

- In the analyses of the primary and secondary outcomes as detailed above, we will exclude patients without outcome data. This approach corresponds to missing completely at random (MCAR).
- Under the missing at random (MAR) assumption, we will use Markov Chain Monte Carlo (MCMC) for multiple imputation approach with 20 imputed copies. Standard multiple imputation methods will be adopted.
- Under the missing not at random (MNAR) assumption, we will use the following methods.
 - Best-case and worst-case scenario analysis: For binary outcomes, we will impute all missing outcomes as successes in the intervention group and failures in the control group for the best-case scenario and the opposite for the worst-case scenario.
 - Pattern-mixture models: These models will be used to explore the impact of different missing data patterns on the results.
 - Selection models: We will fit models that make specific assumptions about the mechanism of missingness, such as logistic regression models that include a term for whether data are missing or observed.

Analysis based on the per-protocol population

The above specified analyses for the primary and secondary outcomes will be repeated using the per-protocol population.

Reporting of Sensitivity Analyses:

- Results will be reported focusing any changes in significance or the magnitude of the treatment effect compared to the results of the primary analyses specified above.

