- Each secondary outcome will be listed with its respective statistical analysis results.
- We plan to move this table to supplementary material as we plan to present the results using a forest plot. The final decision will depend on the journal style.

Table 4: Safety Outcomes

- This table will list all adverse events and serious adverse events reported during the trial. If there are too many AEs to include in the main text, this table will be moved to the supplementary material.
- The table will include rows for each type of adverse event and columns for the intervention group, control group, number of events, percentages, and a comparison column if appropriate.

Figure 1: CONSORT Flow Diagram

- The flow diagram will provide a visual representation of participant flow through the trial, including enrollment, allocation, follow-up, and analysis.
- It will have boxes for each phase and arrows indicating the movement of participants, with numbers for each group at each stage.

Figure 2: Forest plot of the primary and secondary outcomes.

- This figure will present the results of primary and secondary analyses.
- The forest plot will include lines for each subgroup with squares representing the effect estimate (e.g., odds ratio) and horizontal lines representing the 95% confidence intervals.
- A vertical line will represent no effect, and a diamond at the bottom will represent the overall effect size.
- The style of presentation will be similar to the following figure.

[figure not shown]

Figure 3: Forest Plot for Subgroup Analysis

- This figure will present the results of pre-specified subgroup analyses.
- The forest plot will include lines for each subgroup with squares representing the effect estimate (e.g., odds ratio) and horizontal lines representing the 95% confidence intervals.
- A vertical line will represent no effect, and a diamond at the bottom will represent the overall effect size.

Appendices

Inclusion of the SAP approval form, mock tables and figures, and any relevant statistical code.

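### The SAP gives the same safety display two scopes: procedure-related events in the Safety analysis section, all reported events in Table 4

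*SAP*

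**What the plan says.** Five parts of the SAP bear on this point.

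- **Safety analysis.** "This analysis will list all adverse events and serious adverse events that were related to the research procedures". The layout has a row per event type and "columns for the intervention group, control group, number of events, percentages, and a comparison column if appropriate".
- **Tables and Figures, Table 4: Safety Outcomes.** "This table will list all adverse events and serious adverse events reported during the trial". The layout is described in the same words as in the Safety analysis section, with no mention of relatedness.
- **Safety Measures, Adverse Events (AE).** The definition is causality-neutral, "including occurrences which are not necessarily caused by or related to that intervention". Safety is to be monitored by "recording acute adverse events at 24 hours and 30 days after randomization as a trial outcome", with entry on the case report form.
- **Safety Measures, Serious Adverse Event (SAE).** An event is related if "it resulted from administration of any of the research procedures", in the Chief Investigator's opinion. Only complications judged related to study procedures "and not a typical surgical complication should be reported as SAEs".
- **Analysis Populations.** "The per-protocol population will be used in the safety and sensitivity analysis". The Table 4 shell names no population.

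**The concern.** Two analysts working from this SAP could produce different safety tables and each claim to have followed it. One would select events by attributed cause and the other would not. Preventing that kind of divergence is a main purpose of an SAP.

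The related-only scope is also the weaker choice for a table with one column per arm. Selecting events by attribution replaces a comparison of randomized groups with a comparison of judgements about them. The SAP does not say whether that judgement is masked (the protocol may). Guided care leads to treatment actions that usual care does not, so harm from those actions can be called related in one arm only. The resulting error could go either way. The intervention column could look worse because the control column has fewer routes to a related event. Or harm that resembles the ordinary course after surgery could be judged unrelated and dropped from the table.

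**Working it through.** The point rests on wording. It uses no alpha, power, rate or event count, so there is no figure to reproduce. The check sets the sections side by side.

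**Step 1: is it one display or two?** The Safety analysis section and Table 4 give the same rows, the same columns and the same optional comparison column. Nothing suggests that two tables are meant. This is one display with two stated scopes.

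**Step 2: what does each scope contain?** The sentence in the Safety analysis section can be read in two ways. The relatedness clause may qualify both AEs and SAEs (reading A) or SAEs alone (reading B).

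| | Safety analysis, reading A | Safety analysis, reading B | Table 4 |
|---|---|---|---|
| AEs | related only | all | all reported |
| SAEs | related only | related only | all reported, but already restricted at reporting to related and not typical |

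**Step 3: where do they differ?**

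- AEs: under reading A the two sections conflict directly, because AEs are defined and recorded whatever their cause. Under reading B they agree.
- SAEs: under either reading they largely coincide. The reporting rule in Safety Measures has already removed unrelated and typical events, so a further relatedness filter takes out little or nothing.

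The conflict therefore concerns the AE rows, and it depends on a reading that the text does not settle.

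**Step 4: can the filter act unequally between arms?** Relatedness is tied to research procedures in general, and the SAP does not list which of these the usual-care arm undergoes. The Subgroup Analyses section divides patients by each patient's median cerebral and somatic tissue oxygen saturation and plans odds ratios by subgroup. That suggests control patients have saturation data too, so an event caused by a sensor could arise in either arm. An event caused by an action that the guidance prompted could arise in the intervention arm only. Some inequality is therefore possible. Its size depends on counts that the SAP does not give.

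**Step 5: what is compared elsewhere without this filter?** Under Objectives and Endpoints, the primary composite covers death and brain, cardiac, respiratory, renal and infectious complications of Clavien-Dindo grade II or above. Its components, atrial fibrillation, delirium, cognitive decline and length of stay are secondary outcomes. All have their primary analysis in the intention-to-treat population with no relatedness condition. What remains is milder events and event types outside those lists. For these, the safety table is the only between-arm display that the SAP describes.

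**The case against.** The case for leaving the text alone has real force. On reading B the sections are compatible. For SAEs they hardly differ on any reading. The comparison column is optional and the displays are described as templates, so no formal safety test is promised. The harms that matter most are already compared as efficacy outcomes.

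Most of this stands, and it limits the consequence. It does not remove the problem. The sentence does not say which reading is meant, and an optional comparison of a selected set of events is still selected.

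A reader might draw three stronger conclusions that the document does not support:

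- *That related events in the control arm must be close to zero by definition.* The SAP does not list the research procedures in usual care, and the saturation subgroups suggest that controls were monitored as well.
- *That harms resembling ordinary surgical complications would never be compared.* Most serious harms of that kind fall within the primary composite or the secondary outcomes, which are compared by arm regardless of cause.
- *That the SAP classes most complications as unrelated.* It says that complications are expected and restricts which are reported as SAEs. It gives no proportion.

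**Conclusion.** The inconsistency is real and should be corrected, and its reach is moderate. The SAP fixes two scopes for one safety display. On the more natural reading, the narrower scope contradicts the SAP's own definition and recording of AEs, and it makes the display depend on a post-randomization causality judgement that can fall unequally on the arms. The number of events affected and the direction of any distortion cannot be given from the document.

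The consequence is confined to adverse events outside the primary composite, its components and the other secondary outcomes. This conclusion assumes that AEs were recorded on the case report form without regard to cause, as the Adverse Events section states. It also assumes that guidance-prompted actions are specific to the intervention arm, which follows from the comparison of guided with usual care.

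**What to change.** State one scope in the Safety analysis section and in Table 4:

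1. Tabulate all recorded AEs by arm, giving both the number of patients with an event and the number of events.
2. Show relatedness as a sub-row or an added column, not as a condition for entering the table.
3. If a between-arm comparison is made, make it on all recorded AEs.
4. Footnote the SAE rows to say that SAEs were reported only if judged related to study procedures and not a typical surgical complication, so those rows are not an unfiltered comparison. Changing the table wording alone cannot recover SAEs that this rule kept from being reported.
5. Name the analysis population on the table. The Analysis Populations section assigns safety to the per-protocol population. The table should agree with that statement, or any change of population should be made openly in both places.

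The cost is SAP wording and a longer table. The AE rows need no new data, because the SAP says AEs are already entered on the case report form.

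### As worded, the SAP's example selection model cannot assess MNAR for patients whose outcome is wholly missing, and nothing graded is specified between the best-case and worst-case bounds

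*SAP*

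**What the plan says.** All of this is in the SAP under Sensitivity Analysis, Missing Data, unless noted.

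- What is missing is the outcome: "These analyses deal with the patients who did not have outcome data".
- Main analyses: "we will exclude patients without outcome data".
- MAR: "we will use Markov Chain Monte Carlo (MCMC) for multiple imputation approach with 20 imputed copies".
- MNAR: "Under the missing not at random (MNAR) assumption, we will use the following methods". Three methods follow:
  - Best and worst case: "we will impute all missing outcomes as successes in the intervention group and failures in the control group for the best-case scenario", with the reverse for the worst case.
  - Pattern-mixture models, with no offsets stated.
  - "Selection models: We will fit models that make specific assumptions about the mechanism of missingness", followed by the example "such as logistic regression models that include a term for whether data are missing or observed".

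For the selection model, the text names no dependent variable, does not say that missingness depends on the outcome, and gives no sensitivity parameter or range. Elsewhere the SAP uses logistic regression for binary outcomes, as in Analysis of the primary outcome: "The primary outcome will be evaluated using logistic regression to estimate the odds of postoperative composite complications".

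Reporting of Sensitivity Analyses promises to report changes in significance or effect size against the primary results, with a narrative on what they imply.

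**The concern.** A selection model pairs an outcome model with an equation for the probability of being missing, and the possibly unseen outcome is a predictor in that equation. The SAP's example reads differently. A term in a logistic regression is, on its plain meaning, a covariate, and the SAP's other logistic regressions have the clinical outcome as response. A missing/observed covariate can tell us something only if outcomes are known at both of its values, and for a wholly missing outcome they are not.

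The risk is to interpretation. A model that returns the complete-case or MAR estimate would show no change under the SAP's reporting rule, and a reader could take that as robustness to MNAR although MNAR was never examined.

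**Working it through.** The SAP states no figure for this item, so there is none to reproduce. The check is about identifiability, with one simulated data set as illustration.

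**Inputs.** From Sample Size Determination: 980 per group, 30% versus 24%, about 5% dropout or missing data. From Analysis of the primary outcome: final critical value -1.932. Assumed for the simulation only: outcomes missing with probability 4%, rising to 12% for events in the intervention arm. This gave 115 missing of 1,960 (5.9%). Y is the composite, T is treatment, and M = 1 if Y is missing.

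**Step 1: outcome as response, observed data.** The model is logit P(Y=1) = α + βT + γM. Every analysed patient has M = 0, so the M column is all zeros (coded the other way, it equals the intercept). The design has rank 2 of 3 and γ is not estimable. The treatment log odds ratio was -0.3585 (SE 0.1055) both with and without M.

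**Step 2: outcome as response, after MAR imputation.** Missing outcomes are drawn from the distribution fitted to observed patients. Given the imputation variables, γ is therefore zero in expectation by construction. The table shows averages over 200 imputations, using treatment only.

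| Same model fitted to | γ | Treatment log OR |
|---|---|---|
| MAR-imputed data | -0.00007 | -0.364 |
| Full simulated data | 0.56 | -0.258 |

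The non-random missingness built into the data leaves no trace in the imputed fit.

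**Step 3: missingness as response.** The model is logit P(M=1) = a_T + δY. Each arm supplies three counts (observed events, observed non-events, missing), which is two free proportions. There are three unknowns per arm: the event rate, the missingness intercept and δ. With δ fixed at a common value in both arms (the range is an assumption):

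| δ | Log-likelihood | Treatment log OR |
|---|---|---|
| -2 | -1509.2461 | -0.366 |
| -1 | -1509.2461 | -0.365 |
| 0 | -1509.2461 | -0.359 |
| 1 | -1509.2461 | -0.341 |
| 2 | -1509.2461 | -0.313 |

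The likelihood is flat, so these data cannot choose δ. The treatment estimate does move with δ, so this form is informative once values are fixed. The SAP fixes none.

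**Step 4: what the best-case and worst-case bounds leave open.** Assume 5% missing per arm: 0.05 × 980 = 49 missing, 931 observed. Take the observed rates at the design values. The whole-arm rate is 0.95p + 0.05q, where p is the observed rate and q the unknown rate among the missing.

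- Intervention: 0.95 × 24% = 22.8% (q = 0), up to 27.8% (q = 1).
- Control: 0.95 × 30% = 28.5% (q = 0), up to 33.5% (q = 1).

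Unadjusted pooled Z:

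- Complete case: SE = √(2 × 0.27 × 0.73 / 931) = 0.02058.
- Both bounds: pooled rate 0.2815, SE = √(2 × 0.2815 × 0.7185 / 980) = 0.02032.

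| Scenario | Intervention | Control | Difference | Z |
|---|---|---|---|---|
| Complete case | 24.0% | 30.0% | -6.0 points | -2.92 |
| Worst case | 27.8% | 28.5% | -0.7 points | -0.34 |
| Best case | 22.8% | 33.5% | -10.7 points | -5.27 |

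The bounds fall on both sides of -1.932. They show that MNAR could matter but not how strong it would have to be.

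**The case against.** Several points on the other side stand.

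- **The response variable is not named, and the logistic model is only an example.** A reader might infer that the SAP commits to an outcome regression with a missingness covariate. The text does not settle that. The governing clause, on assumptions about the mechanism, fits a proper selection model, and a logistic equation for missing versus observed is its usual component. On that reading the defect becomes an unstated sensitivity range, as in Step 3. Fixing values would be consistent with the clause, but none appear.
- **Partial follow-up can make an indicator vary.** Analysis Populations includes randomised patients with partial outcome data and keeps those lost to follow-up until they dropped out. A patient with an early event who is later lost has a known composite, and cognition may be known on day 5 but not day 30. The aliasing in Step 1 therefore applies only to wholly missing outcomes. An indicator that varies among patients with known outcomes still says nothing about those with none.
- **MNAR is not left untested.** A reader might infer that the SAP has no working MNAR analysis. It has one: best-case and worst-case imputation is computable and bounds MNAR for binary outcomes.
- **The size is easily overstated.** A reader might say that each arm's rate can shift by 5 points. Five points is the width of each range. From the observed rate, control can move by -1.5 to +3.5 points and intervention by -1.2 to +3.8. The 5% is also a design allowance that includes dropouts, and the SAP excludes voluntary withdrawals from analysis, so fewer outcomes may be missing.
- **Step 3 used treatment as the only covariate.** Adding covariates could give δ some apparent identification, but only through assumptions of model form that the SAP does not state.

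**Conclusion.** The point holds as a minor to moderate correction to a sensitivity analysis. For wholly missing outcomes, the one concrete model named for the selection-model item does not assess MNAR on any reading. With the outcome as response it is either not estimable or returns the MAR answer; with missingness as response it needs fixed values that the SAP does not give. This goes beyond missing detail, because the example on its plain wording is the wrong tool.

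It affects one of three MNAR methods. The primary estimate, test and error rate do not change. The practical gap is the region between a 0.7-point and a 10.7-point difference, where neither this model nor the pattern-mixture item without offsets offers a graded answer. Those figures assume 5% missing in each arm and observed rates equal to the design rates. The simulation is a single data set with an assumed mechanism: it illustrates the algebra and does not estimate bias in this trial. That the result would be presented as evidence of robustness is a risk, not something the SAP says.

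**What to change.** Replace the example with delta-adjusted (tipping-point) multiple imputation of the composite. Use the planned imputation model and its 20 copies, and shift the imputed log-odds separately in each arm over a prespecified grid. Odds ratios of 0.5 to 3 for missing versus observed patients would be one illustration; the range is for the trial team to justify. Redraw the imputed outcomes at each grid point, check that a zero shift in both arms reproduces the MAR result, and report the combinations at which Z crosses -1.932. This would also give the pattern-mixture item the offsets it lacks.

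If a selection model is kept, state it in full: missingness as response, outcome and treatment as predictors, and prespecified values for the outcome coefficient, by arm if wanted.

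Best-case and worst-case imputation can stay as it is. The cost is one SAP sentence and a short program; no new data are needed.
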